7.2.5 Sponsor Responsibility for Reporting Adverse Events

All AEs will be reported to regulatory authorities, IRB/IECs, and investigators in accordance with all applicable global laws and regulations.

8.0 STATISTICAL ANALYSIS PLAN

8.1 Statistical Analysis Plan Summary

Sample Size: For the TNBC cohort, the null and alternate hypotheses are 19% ORR⁷⁸ and 39% ORR, respectively. For the NSCLC cohort, the null and alternate hypotheses are 20% ORR⁷⁹ and 40% ORR, respectively. For the TNBC cohort, the target response rate is 39%. With a sample size of 28 patients, if the observed number of responders is 11 (39.3%); the 95% CI estimate will have a margin of error of 18.1 percentage points (i.e., 21.2% to 57.4%) based on the normal approximation. For the NSCLC cohort, the target response rate is 40%. With a sample size of 29 patients, if the observed number of responders is 12 (41.4%); the 95% CI estimate will have a margin of error of 17.9 percentage points (i.e., 23.5% to 59.3%) based on the normal approximation. For both the TNBC and NSCLC cohorts, we will implement a safety run-in period for the initial subjects enrolled onto the study. An initial cohort of 3 patients will be followed for toxicity through the first cycle of pembrolizumab. **The PI will submit a status update for the first 3 patients after each individual is enrolled onto this trial via a Reportable Event application.** If only 1 of 3 patients experience toxicity, then 3 more patients will be enrolled. If no more than 1 of 6 patients experience toxicity, then the trial will be fully opened. The staggering interval will be 5 weeks for the run-in cohort.

Statistical Analysis: DoR, OS rate, PFS rate, and CBR will be analyzed. Safety profiles will also be assessed through summaries of AEs, SAEs, AEs leading to treatment discontinuation, and treatment-related death. The safety analysis will report the frequency of all AEs and laboratory abnormalities as well as the frequency of dose interruptions and toxicity-related treatment discontinuation. Toxicity rates will be presented using the worst NCI CTCAE grade per patient.

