4.2.3 Rationale for Endpoints

4.2.3.1 Efficacy Endpoints

The primary efficacy endpoint will be the ORR of ADV/HSV-tk + valacyclovir therapy and SBRT followed by pembrolizumab in patients with metastatic TNBC and metastatic NSCLC. Secondary efficacy endpoints are antitumor activity (RECIST 1.1 in addition to modified irRC), DoR, OS rate, PFS rate, and CBR.

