5.2.3 Second Course

All subjects who stop pembrolizumab treatment with CR may be eligible for up to an additional 12 months (17 cycles) of pembrolizumab treatment if they progress after stopping pembrolizumab from the initial treatment phase. This retreatment is termed the Second Course Phase of this trial and is only available if the trial remains open and the subject meets the following conditions:

Either

- Stopped initial treatment with pembrolizumab after attaining an investigator-determined confirmed CR based on the RECIST 1.1, and
 - Was treated with at least 8 cycles of pembrolizumab before discontinuing treatment, and
 - Received at least 2 cycles of pembrolizumab beyond the date when the initial CR was declared

OR

- Had CR and stopped pembrolizumab treatment after completion of 24 months (35 cycles) of pembrolizumab for reasons other than disease progression or intolerability

AND

- Experienced an investigator-determined radiographic disease progression by the RECIST 1.1 after stopping initial pembrolizumab treatment, and
 - No new anticancer treatment was administered after the last dose of pembrolizumab, and

- The subject meets all of the safety parameters listed in the inclusion criteria and none of the safety parameters listed in the exclusion criteria, and
- The study is ongoing

An objective response or disease progression that occurs during the Second Course Phase for a subject will not be counted as an event for the primary analysis of either endpoint in this trial.

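### Section 8.1 gives only a normal-approximation 95% interval for the primary ORR; at 28 and 29 patients it covers about 91–94% at the design rates, and an exact interval should replace it

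*Combined protocol and SAP*

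**What the plan says.** Section 4.2.3.1 fixes the endpoint: "The primary efficacy endpoint will be the ORR of ADV/HSV-tk + valacyclovir therapy and SBRT followed by pembrolizumab". The statistical plan is Section 8.1.

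Its sample-size paragraph opens with hypotheses: "For the TNBC cohort, the null and alternate hypotheses are 19% ORR" against 39%, and "For the NSCLC cohort, the null and alternate hypotheses are 20% ORR" against 40%. The sizes are then supported by interval width alone. For TNBC, with 11 responders among 28, "the 95% CI estimate will have a margin of error of 18.1 percentage points (i.e., 21.2% to 57.4%) based on the normal approximation". For NSCLC, with 12 among 29, "the 95% CI estimate will have a margin of error of 17.9 percentage points (i.e., 23.5% to 59.3%) based on the normal approximation".

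No significance level, power, test or required number of responders follows. The analysis paragraph begins "DoR, OS rate, PFS rate, and CBR will be analyzed" and goes on to safety; ORR is not in the list. Section 5.2.3, on retreatment, says that second-course responses and progressions "will not be counted as an event for the primary analysis of either endpoint in this trial", so a primary analysis is presupposed, but 8.1 does not describe one.

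**The concern.** The normal-approximation interval is symmetric around the observed proportion and takes its standard error from that proportion. When the observed count is low, the estimated standard error is small too, so the interval is short exactly where it needs to reach upwards. With fewer than 30 patients and response rates of 19–40%, this can bring coverage below the nominal level.

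Because 8.1 names no other method for ORR, this one is the natural default for the report. If it is used, the published interval for the primary endpoint will miss the true rate more often than 5% of the time, and mostly by understating how high the ORR could be. The stated hypotheses also have no decision rule attached, so the plan does not say what interval result would count as beating the null.

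**Working it through.** **Inputs, all from Section 8.1.** TNBC: n=28, null 19%, alternative 39%, illustration 11/28. NSCLC: n=29, null 20%, alternative 40%, illustration 12/29.

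**Step 1: reproduce the plan's intervals.** Formula: p̂ ± 1.96·√(p̂(1−p̂)/n).
- 11/28: 0.3929 ± 1.96·√(0.3929·0.6071/28) = 0.3929 ± 1.96·0.0923 = 39.3% ± 18.1 points, or 21.2–57.4%.
- 12/29: 0.4138 ± 1.96·√(0.4138·0.5862/29) = 0.4138 ± 1.96·0.0915 = 41.4% ± 17.9 points, or 23.5–59.3%.

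Both match.

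**Step 2: exact coverage.** For a true rate p, coverage is the sum of the Binomial(n, p) probabilities over all counts x whose interval contains p. The exact (Clopper-Pearson) limits are the 2.5% quantile of Beta(x, n−x+1) and the 97.5% quantile of Beta(x+1, n−x). *Below* means the whole interval lies under the true rate; *above* means it lies over it.

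| n, true ORR | Normal: counts that cover | Coverage | Below / above | Exact: counts that cover | Coverage | Below / above |
|---|---|---|---|---|---|---|
| 28, 19% | 3–10 | 91.2% | 7.8 / 1.0% | 2–10 | 96.9% | 2.1 / 1.0% |
| 28, 39% | 7–16 | 94.4% | 4.0 / 1.6% | 6–16 | 96.9% | 1.5 / 1.6% |
| 29, 20% | 3–10 | 92.8% | 5.2 / 2.0% | 2–10 | 96.8% | 1.3 / 2.0% |
| 29, 40% | 8–16 | 91.0% | 5.7 / 3.3% | 7–17 | 96.3% | 2.3 / 1.35% |

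In the first three rows the whole difference is one count at the low end. For example, 2/28 gives a normal interval of −2.4% to 16.7%, which misses 19%; the exact interval is 0.9–23.5%. In the last row both ends contribute. At 7/29 the normal upper limit is 39.7%, just short of 40% (exact 43.5%). At 17/29 the normal lower limit is 40.7%, just over 40% (exact 38.9%). Of the 5.3-point gap in that row, 5.7 − 2.3 = 3.4 points come from the upper limit and 3.3 − 1.35 = about 1.9 from the lower.

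**Step 3: is this only a feature of four chosen rates?** Coverage is jagged in p. With n=29 it is 94.5% at ORR 39% and 91.0% at 40%; with n=28 it reaches 95.1% at 36%. Averaged evenly over ORR 15–45%, it is about 92.6% at either sample size.

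**Step 4: planning intervals by the exact method.** 11/28 gives 21.5–59.4% and 12/29 gives 23.5–61.1%. Widths are 37.9 and 37.5 points, against 36.2 and 35.9 for the normal approximation, so about 1.7 points wider.

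**Step 5: the rule that matches the exact interval.** The criterion is that the lower 95% limit exceeds the null.
- TNBC, null 19%: the exact lower limit is 18.6% at 10/28 and 21.5% at 11/28, so at least 11 responders are needed. Alpha = P(X≥11 | 28, 0.19) = 1.0%; power = P(X≥11 | 28, 0.39) = 55.9%.
- NSCLC, null 20%: the exact lower limit is 17.9% at 10/29 and 20.7% at 11/29, so again at least 11. Alpha = P(X≥11 | 29, 0.20) = 2.0%; power = P(X≥11 | 29, 0.40) = 65.7%.

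The normal approximation gives the same cut-offs: its lower limits are 18.0% and 21.2% at 10 and 11 of 28, and 17.2% and 20.3% at 10 and 11 of 29.

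**The case against.** The strongest reply is that these intervals sit in the sample-size paragraph, introduced conditionally on an assumed number of responders. They illustrate precision, their arithmetic is correct, and nothing commits the final analysis to them. That stands: the shortfall is a property of the method, and it reaches the results only if the method is carried forward.

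A second reply is that single-rate coverage figures depend on the discreteness of the binomial and that 91.0% is a local low. That is partly right, and at the TNBC target the value is 94.4%, close to nominal. The average of about 92.6% shows that a shortfall remains.

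A third is that an uncontrolled phase II study may be meant as estimation only. That is a fair reading, but 8.1 states null and alternative rates and does not say that no test is intended.

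Three stronger readings are tempting and are not supported:
- A reader might infer that the normal approximation inflates false success claims. It does not: it and the exact interval both first exclude the null at 11 responders in each cohort.
- A reader might infer that the choice of interval decides the TNBC result at 10/28. Both the method the plan names and the exact interval include 19% there. A conflict arises only with a further method, such as Wilson, that the plan never mentions.
- A reader might infer that the trial misses its own power target. The sizes fit a one-sided 5%, 80%-power normal-approximation formula (27.87 and 28.64, rounded up), but the documents state neither level.

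**Conclusion.** The concern holds in a limited form. The only interval method 8.1 names for the primary endpoint covers 91.0–94.4% at the four design rates and about 92.6% on average over ORR 15–45%, against a nominal 95%. The misses come mainly from an upper limit that is too low. At n=29 and ORR 40% the lower limit also contributes, with 3.3% of intervals lying above the truth against 1.35% for the exact method, so the lower limit cannot be called unaffected.

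The shortfall is moderate and conditional on the planning method being used in the report. The absence of ORR from the analysis paragraph, and of a decision rule for the stated hypotheses, is a gap in the same section that the same edit can close.

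The figures assume independent responses, a common response rate within each cohort, and all 28 and 29 patients in the denominators. The 15–45% averaging range is a choice made for this check, not a figure from the documents.

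**What to change.** In Section 8.1:
- List ORR, per cohort, as the primary analysis, reported with an exact (Clopper-Pearson) 95% interval.
- Replace the planning intervals with 21.5–59.4% (11/28) and 23.5–61.1% (12/29), and remove the reference to the normal approximation.
- Since hypotheses are stated, add the rule that matches this interval, namely that the lower exact 95% limit exceeds the null: at least 11/28 (exact alpha 1.0%, power 55.9%) and at least 11/29 (2.0%, 65.7%). Otherwise, state that the ORRs are estimates and that no formal test is planned.

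Cost: wording only, with no added patients or scans. The intervals become about 1.7 points wider at the planning values and are slightly conservative (96.3–96.9% coverage at the design rates). If the rule is adopted, the plan will show openly that power is below 80% in both cohorts.

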9.0 LABELING, PACKAGING, STORAGE, AND RETURN OF CLINICAL SUPPLIES

9.1 Investigational Product

The investigator shall take responsibility for and shall take all steps to maintain appropriate records and ensure appropriate supply, storage, handling, distribution, and usage of investigational products in accordance with the protocol and any applicable laws and regulations.

Pembrolizumab will be provided by Merck as summarized in Table 7.

Table 7 Product Descriptions

Product Name & Potency	Dosage Form
Pembrolizumab 50 mg	Lyophilized Powder for Injection
Pembrolizumab 100 mg/4 mL	Solution for Injection

9.2 Packaging and Labeling Information

Investigational products will be affixed with a clinical label in accordance with regulatory requirements.

9.3 Investigational Product Disclosure

This trial is open label; therefore, the subject, trial site personnel, Sponsor, and/or designee are not blinded to treatment. Drug identity (name, strength) is included in the label text; random code/disclosure envelopes or lists are not provided.

9.4 Storage and Handling Requirements

Investigational products must be stored in a secure, limited-access location under the storage conditions specified on the label.

Receipt and dispensing of trial medication must be recorded by an authorized person at the trial site.

Investigational products may not be used for any purpose other than that stated in the protocol.

9.5 Returns and Reconciliation

The investigator is responsible for keeping accurate records of the investigational product received from Merck or designee, the amount dispensed to and returned by the subjects, and the amount remaining at the conclusion of the trial.

Upon completion or termination of the study, all unused and/or partially used investigational products will be destroyed at the site per institutional policy. It is the investigator's responsibility to arrange for disposal of all empty containers, provided that procedures for proper disposal have been established according to applicable federal, state, local, and institutional guidelines and procedures and that appropriate records of disposal are kept.

10.0 ADMINISTRATIVE AND REGULATORY DETAILS

10.1 Compliance with Trial Registration and Results Posting Requirements

Under the terms of the FDA Modernization Act and FDA Amendments Act, the Sponsor of the trial is solely responsible for determining whether the trial and its results are subject to the requirements for submission to the Clinical Trials Data Bank, <http://www.clinicaltrials.gov>.

Information posted will allow subjects to identify potentially appropriate trials for their disease conditions and pursue participation by calling a central contact number for further information on appropriate trial locations and trial site contact information.

10.2 Data Management

CRFs will be designed and utilized to capture all patient data. An electronic database will be designed to store patient CRFs. Data quality control will be performed regularly by the research coordinator/research nurse to ensure timely, accurate, and complete patient data collection. Queries will be generated and resolved prior to the generation of interim and final summary reports.

12.0 APPENDICES

12.1 ECOG Performance Status Scale

Grade	Description
0	Normal activity. Fully active, able to carry on all pre-disease performance without restriction.
1	Symptoms, but ambulatory. Restricted in physically strenuous activity, but ambulatory and able to carry out work of a light or sedentary nature (e.g., light housework, office work).
2	In bed <50% of the time. Ambulatory and capable of all self-care, but unable to carry out any work activities. Up and about more than 50% of waking hours.
3	In bed >50% of the time. Capable of only limited self-care, confined to bed or chair more than 50% of waking hours.
4	100% bedridden. Completely disabled. Cannot carry on any self-care. Totally confined to bed or chair.
5	Dead.

12.2 Common Terminology Criteria for Adverse Events V4.03

The descriptions and grading scales found in the revised NCI CTCAE version 4.03 will be utilized for AE reporting. (<http://evs.nci.nih.gov/ftp1/CTCAE/About.html>)

12.3 Modified irRC (derived from RECIST 1.1)

Overall responses derived from changes in index, non-index, and new lesions

Measurable Response	Non-Measurable Response		Overall Response Using Modified irRC
Index and New, Measurable Lesions (Tumor Burden)	Non-Index Lesions	New, Non-Measurable Lesions	
Decrease 100%	Absent	Absent	irCR*
Decrease 100%	Stable	Any	irPR*
Decrease 100%	Unequivocal progression	Any	irPR*
Decrease \geq 30%	Absent / Stable	Any	irPR*
Decrease \geq 30%	Unequivocal progression	Any	irPR*
Decrease $<$ 30% to increase $<$ 20%	Absent / Stable	Any	irSD
Decrease $<$ 30% to increase $<$ 20%	Unequivocal progression	Any	irSD
Increase \geq 20%	Any	Any	irPD

*Assuming that the response (irCR and irPR) and progression (irPD) are confirmed by a second, consecutive assessment at least 4 weeks apart.

irCR, immune-related complete response; irPR, immune-related partial response; irSD, immune-related stable disease; irPD, immune-related progressive disease.

12.4 New York Heart Association Functional Classifications

Class	Description
I	Patients with cardiac disease but without resulting limitations of physical activity. Ordinary physical activity does not cause undue fatigue, palpitation, dyspnea, or anginal pain.
II	Patients with cardiac disease resulting in slight limitation of physical activity. They are comfortable at rest. Ordinary physical activity results in fatigue, palpitation, dyspnea, or anginal pain.
III	Patients with cardiac disease resulting in marked limitation of physical activity. They are comfortable at rest. Less than ordinary physical activity causes fatigue, palpitation, dyspnea, or anginal pain.
IV	Patients with cardiac disease resulting in inability to carry on physical activity without discomfort. Symptoms of cardiac insufficiency or of angina syndrome may be present at rest. If any physical activity is undertaken, discomfort is increased.
